Mental health services in Nigeria are deficient in quantity and quality. It is estimated that there is currently one psychiatrist to one million inhabitants and 40:1,000,000 for psychiatric nurses. [21] Furthermore, distribution of the available professionals is grossly skewed in favour of urban areas. The organization of mental health services is top-heavy; at the apex of the pyramid are 8 federal neuro-psychiatric hospitals and about 20 departments of Psychiatry at University Teaching Hospitals. Referral systems are cumbersome and not patient-friendly. Health workers at the secondary and primary levels including Doctors and Nurses have little practical training in or awareness of mental health issues. This leaves majority of rural dwellers who constitute majority of the population underserved. The notion of universal coverage and the Sustainable Development Goal mantra of 'leaving no one behind' will remain unattainable if these circumstances persist.

Study design

This is a cluster-randomized trial involving ten LGAs with the highest number of notified leprosy or BU cases between 2014 and 2018, purposively selected from 220 LGAs in south-east/south-south Nigeria. Five LGAs namely, Ebonyi, Ogoja, Ogbaru, Ogbia and Calabar South were randomized as intervention LGAs and five comparable LGAs – Etinan, Ethiope East, Obubra, Anambra East and Isoko South will serve as control. For allocation of clusters (LGAs) to intervention and control groups, a computer-generated list of random numbers was used.

Baseline survey will be done in the first year of the project in both intervention and control LGAs to determine the magnitude of depression using Patient Health Questionnaire-9 (PHQ-9); generalized anxiety disorders using Generalized Anxiety Disorders-7 (GAD-7), self-stigma using Stigma Assessment and Reduction of Impact (SARI) scale and quality of life using WHOQOL-BREF and Warwick-Edinburgh Mental Well-being Scale (WEMWBS) among eligible persons affected by leprosy/BU.

Attitude of health workers and community leaders towards leprosy/BU patients will be assessed using Focus Group Discussions (FGDs) and Key Informant Interviews (KII). Additionally, social distance scale (SDS) will also be used for community leaders.

Intervention

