The intervention will be at three different levels expected to work synergistically with the intention to reduce mental disorders and improve quality of life among persons affected by leprosy/BU. Therefore, the intervention will include the following:

• Engaging selected community members as lay counselors for basic mental health management:

Advocacy visit to community gate-keepers will provide a platform to identify suitable and willing community leaders who will be trained to serve as lay counsellors for persons affected by leprosy/BU. Depending on the size of each LGA, at least 5 persons will be selected per LGA so that leprosy/BU patients will not need to travel long distances to access care. Following baseline assessment of their perception by trained research assistants using the social distance scale (SDS) and FGDs, their capacity as lay counsellors for the identification and basic management of depression and general anxiety disorders will be built. The 3-day training will be facilitated by Psychiatrists/Clinical Psychologists, Leprosy/BU programme team and Person affected by NTD. Topics to be covered include: i) basic facts about leprosy and BU; ii) screening for depression and GAD using PHQ-9 and GAD-7; iii) basic skills for counselling and psychosocial support; iv) need for social inclusion for persons affected by NTDs; and v) team work/appropriate referrals. After the training, they will be supportively supervised to provide counselling services to leprosy/BU patients with mental disorders and promote their social participation in communities. Laycounsellors represent a critical link between the formal health system and patient's selfhelp groups. Supervision will be done through phone calls and online meetings reinforced by quarterly visits and yearly re-training by research team/mental health experts.

Formation of self-help groups (SHG) among persons affected by leprosy or BU.
Persons affected by leprosy/BU will be organized into self-help groups. The SHGs will be for all patients whether they have mental health problems or not. At the outset, a baseline

assessment of level of self-stigmatisation among these persons will be carried out by trained research assistants using the SARI Stigma scale.

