The purpose of forming SHGs is to reduce self-stigma and improve quality of life among them through peer support. During the formation of SHGs, orientation provided by the research team will include objectives and procedures for establishment of self-help groups. Through an interactive discussion, feedback from persons affected by leprosy/BU will inform essential revisions on the protocol and expected deliverables of the SHGs in line with project objectives. Roles of each member as well as strategies for collaboration with identified community leaders and healthcare givers serving each group will be clearly outlined. Thereafter, the standard operating procedures (SOP) for the SHGs finalized. Members of the SHGs will be guided to elect/appoint their group leaders for effective coordination of the SHGs.

Members of SHGs will be trained to provide psychosocial support to each other through: (i) early and prompt identification of group members with features suggestive of depression or GAD, for example those who suddenly withdraw from social gatherings, meeting absentees or share experiences in group meetings related to mental illness; (ii) each member contacting community opinion leaders directly or through SHG leaders for action (iii)participation in bimonthly meetings to share personal experiences and how to overcome them; (iv) regular communication of SHG leaders/members with the healthcare workers or/ and community leaders regarding physical, mental or social needs members of the group; (v) secured interest of members through regular feedbacks/report from SHG leaders to research team regarding patient satisfaction with mental healthcare received from community leaders and health workers, etc.. Home visits to members who are inconsistent in meetings will also be part of their activities. The opportunity of meetings could be used for skill acquisition and they can form cooperative thrift to support each other financially. Depending on the number of patients in each LGA, there could be more than one self-help group with an average of 15 persons which will be based on proximity of participants to each other.

• Training of healthcare workers:

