- Prevalence of mental disorders among persons affected by Leprosy/BU using PHQ-9 as screening tool for depression and GAD-7 (see annex for tools) to screen for GAD.
- Attitude of community leaders towards leprosy/BU patients using SDS and FGD/KII.
- Stigma perception among persons affected by leprosy/BU using SARI Stigma scale
- Quality of life and mental well-being of persons affected by leprosy/ BU using WHOQOL-BREF and WEMWBS.
- Perception of healthcare workers on mental well-being of leprosy/BU patients using FGD/KII.

The study and control groups will be compared after intervention to determine change in mental health status, quality of life and social participation of study participants.

Data quality will be guaranteed by:

- Training and supervision of research assistants
- Double transcription of voice recordings of KIIs and FGDs

Validation of study tools

Prior to field work, a short validation will be done to validate the WEMWBS tool in all relevant study sites in Nigeria.

This involves:

- Translation/back-translation of tool in Pidgin English, Igbo and Efik languages
- Conduct interviews to ascertain how well tool is understood (interpretability).
- Several rounds of translation/back-translation with 5-10 persons.

• Further validation will be done during field work.

Recruitment

To recruit study participants, first, names and contact details of leprosy or BU patients will be obtained from LGA Leprosy and Buruli ulcer Treatment Registers, respectively. Eligible persons will be contacted by phone calls through the LGA Tuberculosis and Leprosy Supervisors (LGTBLS) and invited for orientation meeting on a scheduled date. Newly detected, eligible leprosy or BU patients registered for treatment at the health facilities during intervention will also be evaluated for depression and GAD by healthcare workers using the research tools and thereafter introduced to nearby SHGs. All leprosy/BU patients who are eligible regardless of mental health status will be enrolled into SHGs up to one year before end of intervention. However, patients who come after the deadline will join the SHGs and receive appropriate services, but not included in final research analysis. All suspected cases of BU or leprosy found by community leaders or members of SHGs will be referred to health workers for diagnosis.

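### Allocation is complete and the arms are named before registered patients are invited, consented and surveyed, and no concealment is described, so entry to the baseline cohort and baseline answers can depend on arm

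*Protocol*

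**What the plan says.** The point concerns the cohort already on the registers, not patients newly registered during the intervention.

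- **Allocation (Study design).** It is in the past tense and the areas are named: "Five LGAs namely, Ebonyi, Ogoja, Ogbaru, Ogbia and Calabar South were randomized as intervention LGAs". On the method, "a computer-generated list of random numbers was used".
- **Baseline (Study design).** It is still to come, in areas already labelled by arm: "Baseline survey will be done in the first year of the project in both intervention and control LGAs". The self-stigma scale (SARI) is among the instruments listed there for both arms.
- **Sampling frame and invitation (Recruitment).** First, "names and contact details of leprosy or BU patients will be obtained from LGA Leprosy and Buruli ulcer Treatment Registers". Eligible people are then telephoned "through the LGA Tuberculosis and Leprosy Supervisors (LGTBLS) and invited for orientation meeting on a scheduled date". The text does not say what the meeting covers or whether it is the same in both arms. The same paragraph goes on: "All leprosy/BU patients who are eligible regardless of mental health status will be enrolled into SHGs", with no arm stated.
- **Orientation (Intervention, self-help groups).** "During the formation of SHGs, orientation provided by the research team will include objectives and procedures for establishment of self-help groups". The SARI "assessment of level of self-stigmatisation among these persons will be carried out" is described in the same part, in a sentence that places it at the start.
- **Consent.** Ethical considerations has written consent taken ahead of the interview. Refusal is an exclusion criterion.
- **Interviewers (Data management).** There are two research assistants per LGA, drawn from the selected communities. No masking is mentioned.
- **Analysis (Data management).** Arms are compared by chi-square and Student t tests.

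**The concern.** Randomising LGAs balances the arms, apart from chance, only if entry to the cohort does not depend on the allocation. Here everything that decides who enters (the telephone call, attendance and consent) happens after the arms are fixed and named. Recruiters, patients and interviewers may therefore know the arm.

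Two biases could follow. First, a peer-group offer could attract some patients and deter others who fear being seen, and that offer exists in five LGAs only. The protocol's background stresses stigma in the south, so either direction is plausible. Second, PHQ-9, GAD-7 and SARI are self-reported to a local interviewer, so baseline answers could shift if support has been announced. The first bias would pass into the between-arm comparison. The second would pass into the before-and-after comparisons.

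**Working it through.** **1. Order of events.** Set side by side, the sections give: allocation (done), register listing (future), telephone invitation (future), orientation meeting (future), consent (future), interview (future). Nothing says that consent or baseline is completed before the arm is disclosed.

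**2. Who could know the arm.** The protocol does not say outright that supervisors, patients or interviewers know it. It names the arms and describes no step that withholds them.

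**3. What the invitation is to.** Recruitment gives one route for all participants and leaves the meeting undefined. The only patient orientation described anywhere is the SHG one, and the recruitment paragraph runs straight on to SHG enrolment. Control patients have no described SHG to be oriented to. A difference by arm is therefore a reasonable inference, but it is not stated.

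**4. What the register frame protects.** It limits choice over who is listed. It does not govern who attends, who consents or how they answer.

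**5. Possible size.** The plan gives no uptake figure, so there is none to reproduce and the uptake rates below are assumed. True prevalence is taken as p = 0.50 in both arms (the anticipated figure in Sample size calculation). Control uptake does not depend on mental-health status, so control prevalence stays at 50%. In the intervention arm u1 is uptake with a disorder and u0 uptake without:

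prevalence among entrants = p·u1 / (p·u1 + (1 − p)·u0), which at p = 0.50 is u1 / (u1 + u0).

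| u0 | u1 = u0 + 0.05 | u1 = u0 + 0.10 | u1 = u0 + 0.20 |
|---|---|---|---|
| 0.80 | 0.85/1.65 = 51.5% | 0.90/1.70 = 52.9% | 1.00/1.80 = 55.6% |
| 0.70 | 0.75/1.45 = 51.7% | 0.80/1.50 = 53.3% | 0.90/1.60 = 56.3% |
| 0.60 | 0.65/1.25 = 52.0% | 0.70/1.30 = 53.8% | 0.80/1.40 = 57.1% |

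The spurious gap runs from 1.5 to 7.1 points. If people without a disorder respond more, it reverses: 0.80/1.65 = 48.5% at the small end and 0.60/1.40 = 42.9% at the large end.

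**6. Scale against the planned effect.** The planned 35% reduction can be read in three ways:

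- 50% to 35% (15 points): 1.52/15 = 10% to 7.14/15 = 48%.
- A relative reduction, 50% to 32.5% (17.5 points): 1.52/17.5 = 9% to 7.14/17.5 = 41%.
- A fall of 35 points: 1.52/35 = 4% to 7.14/35 = 20%.

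These ratios set a baseline gap against a post-intervention effect. They hold only if the gap persists undiluted and is not adjusted for.

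**The case against.** The strongest reply is that the stated order is baseline first, then intervention, with one recruitment route for everyone from a fixed register frame. Much of this stands, and it rules out several stronger readings.

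- **That intervention patients are known to be invited to an SHG orientation and controls to something else.** A reader might infer this, but no sentence links the orientation meeting in Recruitment to the SHG orientation, and Recruitment does not split by arm.
- **That SARI is answered after patients hear of the SHGs.** Its appearance in the SHG part invites this reading. But that sentence puts the assessment at the start, and Study design lists SARI in the baseline survey of both arms.
- **That supervisors must know the arm because they help choose health workers for training.** Recruitment places that choice during the intervention, so it shows nothing about what they know when patients are telephoned.
- **That the bias cannot be repaired.** This goes too far. PHQ-9, GAD-7 and demographic data are collected in both arms, so measured imbalance can be seen and partly adjusted for. A statistical analysis plan, if one exists, may provide for this. Adjustment does not reach unmeasured differences between attenders and non-attenders, or baseline answers that are themselves distorted.

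It is also true that cluster trials often randomise before recruiting, and that an allocation already made and named may no longer be fully concealable. But this frame consists of existing registers, so a neutral invitation and a complete baseline before any announcement remain feasible. The order of field visits belongs to the protocol, not to an analysis plan.

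**Conclusion.** The concern holds in this form: allocation precedes invitation, consent and baseline, and no concealment is described, so entry and baseline answers can depend on arm. That conclusion rests on the stated sequence. It does not need the inference about the SHG orientation, which would only make matters worse if correct.

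The between-arm tests, as written, do not adjust for baseline. A logistic regression is planned for predictors of outcome, but the protocol does not make it the between-arm comparison. A difference in who enters would therefore pass into the result.

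The size is unknown. Under the assumed uptake gaps of 5 to 20 points it is 1.5 to 7.1 points of baseline prevalence, in either direction; 7.1 is the extreme of that range, not an expected value. The matter should be settled before the first patient is telephoned, because the order cannot be changed afterwards.

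**What to change.** Amend Recruitment so that:

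1. The list of eligible registered patients in all ten LGAs is fixed at one date.
2. One invitation script and the same first meeting are used in both arms, describing the study truthfully without announcing the LGA's arm.
3. Consent and the full baseline, SARI included, are completed in each LGA before the arm is announced there and before any SHG orientation. Community-entry visits still take place but are kept arm-neutral, and allocation is withheld from supervisors and interviewers as far as is still possible.
4. SHG orientation is a separate later meeting in intervention LGAs, with consent to it at that point if the ethics committee requires.
5. Numbers listed, contacted, attending, consenting and surveyed are reported per LGA and arm.

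The cost is protocol wording and a change in the order of field visits, a later SHG start, a second meeting for intervention patients, and possibly a two-stage consent with ethics review. Because the allocation already exists, the change reduces the risk of bias but cannot guarantee its absence. The counts in item 5 would let a reader judge what remains.

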Health workers from primary healthcare units will be trained on screening persons affected by leprosy/BU for mental health problems using PHQ-9, GAD-7 for depression/GAD and WEMWBS for quality of life; providing pharmacological and psychosocial treatment and/or effective referrals to psychiatrists/clinical psychologists for severe cases. Topics covered in the training include those of community lay-counsellors in addition to basic treatment for common mental disorders especially depression and GAD and supportive referrals to appropriate levels of care.

• Inter-linkage of services and collaboration among the three pillars of care:

Healthcare workers and community lay-counsellors will hold joint review meetings with SHGs at agreed locations once every two months. During interactive sessions, project progress will be re-appraised and challenges to optimal mental healthcare, social participation and well-being of leprosy/BU patients in the community addressed. In-between meetings, members/leaders of SHGs who observe features suggestive of mental illness in any member will report same to community lay-counsellor who evaluates and provides basic counselling after documentation. Whenever necessary, the community lay-counsellor contacts the healthcare worker on behalf of the patient and supports patient to receive required attention including chemotherapy or referral to psychiatrist/clinical psychologist through the health worker after documentation. New cases of leprosy/BU who report to facilities will also be referred by healthcare workers to the nearest SHG while providing routine services.

The intervention phase will take 1 to 2 years with quarterly community sensitization during supervisory visits by research team to promote social inclusion, raise awareness on mental health problems and availability of services to create demand and enhance utilization. Re-training of service providers and self-help groups will be done twice throughout the project period. All assessments done at baseline will be repeated post-intervention in both intervention and control groups, to capture any changes. If successful, the project will provide evidence for a holistic, community-oriented approach for improving access and utilization of mental health services which can be scaled-up nationwide.

Study population:

The study involves three key populations: community opinion leaders, healthcare workers and self-help groups of persons affected by leprosy/BU.

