Community opinion leaders will serve as lay-counsellors for patients with mental health disorders. These may include religious leaders, school teachers, retired civil servants, youth and women leaders and other respected members of the community. At least five lay-counsellors will be selected per LGA.

The primary healthcare workers include nurses and community health officers(CHOs). They will work with community leaders to provide mental healthcare in form of pharmacotherapy and psychotherapy to diagnosed patients as well as ensure referral to psychiatrist/clinical psychologist whenever necessary. At least five healthcare workers will be recruited per LGA.

Inclusion criteria

- Any person affected by leprosy/BU
- All persons affected by leprosy/BU registered for treatment from 2014 up to one year before end of intervention.
- Participants aged between 15 to 65 years.

Exclusion criteria

- Refusal to give consent
- Patients who need urgent medical attention
- Patients unable to communicate clearly

Sample size calculation

A study in Nigeria revealed that 58% of leprosy patients have mental disorders. [4] This study anticipates that 50% of respondents will have mental disorders and 35% reduction is desired after intervention. A study demonstrated that training of community lay-workers could reduce prevalence of depression by more than 20%. [15] A World Bank study revealed 22% of Nigerians are depressed.[22] Therefore, sample size calculation for matched pairing at power=80%; p=0.05 and anticipated 30% loss to follow up is 400 leprosy patients (200 each group: intervention/control). Calculation was powered by leprosy alone, because data on mental disorders among BU patients are unavailable. However, it is known that many features (disfigurements and

stigma) known to result in mental health disorders are similar in both diseases. All eligible BU patients will be included.

2.5.6 Data collection methods:

Data will be collected from persons affected by leprosy/BU at baseline and post intervention and from community leaders and healthcare workers in intervention and control LGAs. Data collection tools include: PHQ-9, GAD-7, WEMWBS, SARI stigma scale, WHOQOL-BREF, SDS, FGD/KII guides, Log-books kept by community leaders and SHGs and registers for routine leprosy/BU data collection. Data will include:

- Bio-demographic information

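### Patients registered after allocation can enter the analysis, and the only entry route described runs through intervention components, with no equivalent route or assessor fixed for control LGAs

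*Protocol*

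**What the plan says.** **Allocation is done and known.** Protocol, Study design: "Five LGAs namely, Ebonyi, Ogoja, Ogbaru, Ogbia and Calabar South were randomized as intervention LGAs". The five control LGAs are named there too.

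**Eligibility runs into the intervention period.** Protocol, Inclusion criteria: "All persons affected by leprosy/BU registered for treatment from 2014 up to one year before end of intervention". The criterion does not mention arm.

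**Entry of new cases.** Protocol, Recruitment, starts from the LGA treatment registers. It then adds that new cases "registered for treatment at the health facilities during intervention will also be evaluated for depression and GAD by healthcare workers". In full, they are to be "evaluated for depression and GAD by healthcare workers using the research tools and thereafter introduced to nearby SHGs". Eligible patients, whatever their mental health status, "will be enrolled into SHGs up to one year before end of intervention".

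**Who is left out.** In the same section, "patients who come after the deadline will join the SHGs and receive appropriate services, but not included in final research analysis". New cases before the deadline are therefore, by implication, analysed.

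**Who finds new cases.** Recruitment also states: "All suspected cases of BU or leprosy found by community leaders or members of SHGs will be referred to health workers for diagnosis".

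**What belongs to the intervention.** Protocol, Intervention, lists lay counsellors drawn from community leaders, SHGs, and training of primary-care staff: "Health workers from primary healthcare units will be trained on screening persons affected by leprosy/BU for mental health problems using PHQ-9". The same staff are trained to treat and refer.

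**Measurement and analysis.** Under Data management, two research assistants per LGA administer the questionnaire. Arms are compared by chi-square and Student t tests, and before-after change by McNemar and paired t tests. The Intervention section repeats the baseline assessments in both arms after the intervention.

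**The concern.** Randomising LGAs balances, in expectation, the patients who could be identified before allocation had any influence. It gives no such protection for patients found later, with allocation known, by people who deliver the intervention. Lay counsellors are taught basic facts about leprosy and Buruli ulcer, and community leaders and SHG members refer suspected cases. The intervention may therefore change how many patients, and which ones, are registered in its own LGAs. The protocol sets out no counterpart for control LGAs.

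If new patients differ from those registered since 2014 in their prevalence of depression or anxiety, and enter the two arms in different proportions, the endline comparison mixes the treatment effect with a case-mix difference. An unadjusted chi-square or t test cannot separate the two.

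A second, narrower issue is the entry score. For the baseline cohort it comes from research assistants. For new entrants it appears to come from health workers who also treat. Only depression and anxiety are mentioned at that point, so baseline quality of life and stigma may be missing for new entrants.

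**Working it through.** **1. Are new cases analysed?** Eligibility extends to one year before the intervention ends, and only arrivals after that deadline are excluded. Earlier new cases are therefore in the analysis.

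**2. Is the route the same in both arms?** Registers and health facilities exist in all ten LGAs, and nothing excludes new control registrants. The route actually described, however, goes from facility to health-worker evaluation to SHG, and it ends in an intervention component. Recruitment speaks of selecting health workers for training in each LGA, but the Intervention section defines that training as part of the intervention. No control version is written down.

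**3. How long is the window for new entrants?** Window = intervention duration minus one year. The Summary gives two years: 2 − 1 = about one year of new entries. The Intervention section gives 1 to 2 years. At the lower end, 1 − 1 = about zero. The two statements must be reconciled.

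**4. Size of a shift.** The protocol gives no expected number of new entrants and no prevalence for them, so the inputs here are assumptions. Let f be the share of new entrants in an arm and d the prevalence difference between new and existing patients, taken as equal in the two arms. With no true effect:

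shift = (f_intervention − f_control) × d

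The extreme case f_control = 0 gives, in percentage points:

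| f (intervention) | d = 10 | d = 15 | d = 20 |
|---|---|---|---|
| 10% | 1.0 | 1.5 | 2.0 |
| 20% | 2.0 | 3.0 | 4.0 |
| 30% | 3.0 | 4.5 | 6.0 |

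The sign follows the sign of d. With f = 20% against 10% and d = 20, the shift is 0.10 × 20 = 2.0 points. With equal f and equal case mix it is 0.

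**5. Which f is plausible?** Assume constant registration and equal tracing of old and new cases. Registers from 2014 to a baseline in the first project year (start July 2020) cover about 7 years, against at most 1 year of new entries: 1/(7 + 1) = about 12%. At f = 12% and no control entrants, the shift is 0.12 × 10 = 1.2 to 0.12 × 20 = 2.4 points. Poor tracing of older cases would raise f. Falling national notifications would lower it.

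**6. Against the target effect.** The sample size section anticipates 50% prevalence and a 35% reduction, without saying whether this is relative or absolute. The largest shift in the grid, 6 points, is:
- 6/15 = 40% of the effect if prevalence falls to 35%
- 6/17.5 = 34% if the reduction is relative (50 × 0.35 = 17.5)
- 6/35 = 17% if it is 35 points absolute

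**7. Effect on the test.** Take 200 × (1 − 0.30) = 140 analysed per arm, 50% prevalence in existing patients, no true effect, two-sided 5%, clustering ignored. The standard error of the difference is about √(2 × 0.25/140) = 0.060. When new patients have the lower prevalence, a shift of 1 point gives a rejection rate of about 5.3%, 3 points about 7.9%, and 6 points about 17%. With zero shift it stays at 5%.

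**The case against.** A reader might infer that new cases accumulate only in the intervention arm and that the arms are therefore no longer comparable. The documents do not establish that. The inclusion criterion is arm-neutral, recruitment starts from routine registers, and facility registration is the single entry point. Referrals by community leaders and SHG members only feed into it, so just the extra cases found that way would make intake differ. What can be said is that comparability is not protected.

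A reader might also infer that intervention staff measure the outcome. The protocol does not say so. The health-worker evaluation takes place at entry, before introduction to an SHG. A different assessor at that point affects new entrants' before-after change, not the endline comparison between arms.

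The one-year cut-off also limits the exposure gap, because every analysed entrant has at least a year before the intervention ends. The magnitude rests on assumed inputs and zero control intake. Registration date is known, so restriction or a sensitivity analysis is feasible, and a statistical analysis plan not at hand may provide for it.

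All of this stands and narrows the point. It does not remove it. Eligibility, recruitment and the analysis cut-off are fixed in the protocol itself. They admit patients identified after allocation without fixing one identification rule and assessor for both arms.

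**Conclusion.** The point holds as a gap in the design, not as demonstrated bias. The direction is open and the size unknown. The range of 1-6 points requires 10-30% new entrants in the intervention arm, none in control, and a 10-20 point prevalence difference, none of which is in the protocol. A rough reading of the register period suggests about 12% and 1.2-2.4 points, still with zero control intake. Equal intake with equal case mix gives zero, and a one-year intervention leaves almost no new entrants. The figure of about 40% of the target effect is the extreme corner of the grid and depends on reading the target as 15 points. The change is worth making because it is cheap now, and an unequal intake cannot be reliably undone once the data are collected.

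**What to change.** 1. Define the primary analysis set as patients on the LGA registers from 2014 to one fixed date before the intervention starts, identified and invited by the same rule in all ten LGAs and assessed at baseline by research assistants.
2. Let later registrants join SHGs as the protocol already provides, but analyse them separately as secondary. Identify them from the registers by the same rule in both arms, and have research assistants take their study measurements.
3. Report, by arm, the number on the registers, the number invited and the number taking part.
4. Reconcile the two-year duration in the Summary with the 1 to 2 years in the Intervention section, since the difference decides whether there are new entrants at all.

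The cost is a change of wording in the inclusion criterion, the recruitment text and the analysis set. Later registrants leave the primary analysis, which reduces its numbers a little.
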